# **FUNDING AND SUPPORT IN KIND**

Funders (names and contact details of all organisations providing funding and /or support in kind for this study	GRACE (reg. no. 1189729)
Financial and non-financial support given	Financial support

# **ROLE OF STUDY SPONSOR AND FUNDER**

The study sponsor is the University of Surrey. The sponsor, along with the Royal Surrey NHS Foundation Trust assumes overall responsibility for the initiation and the management of the study the funder provides financial support for the study.

#### STUDY FLOWCHART

Figure 1: Pathway for endometrial cancer patients undergoing surgery for endometrial cancer

[figure not shown]
[figure not shown]

Figure 2: Pathway for patients undergoing chemotherapy for endometrial cancer

#### STUDY PROTOCOL

# Adipocytokines and their relationship with obesity and endometrial cancer

**KEY WORDS:** Endometrial cancer, adiponectin, leptin, TNF  $\alpha$ , IL 6, IGF 1, IGF 2, obesity

#### 1. BACKGROUND

Endometrial cancer is the most common malignancy of the female genital tract. It is the fourth most common cancer in the UK with around 9,500 new cases in 2017, current lifetime risk being 1 in 36 women¹. The number of women diagnosed with endometrial cancer continues to rise each year. Since the early 1990s, uterine cancer incidence rates have increased by almost three-fifths (55%) in the UK (2015-2017)¹. The association between endometrial cancer and obesity is well documented. 7.5% of all cancers in women in UK are attributable to being overweight / obese (BMI ≥25 kg/m2). For endometrial cancer, this risk rises to 34%². A review of meta-analyses showed endometrial cancer risk is 16% higher per 5 kg- gained during adulthood, 29% higher per 10cm increase in hip circumference and 27% higher per 10cm increase in waist circumference³. This higher endometrial cancer risk with raised BMI is present in both pre- and post-menopausal women. Moreover, patients who are obese tend to have a poorer outcome with more comorbidities than their non-obese counterparts.

In the overweight and obese state, the function of the adipose tissue deteriorates resulting in a state of chronic inflammation. In this inflammatory state, adipocytes and macrophages secrete several molecules, adipokines and inflammatory cytokines, which may promote tumour development and angiogenesis and stimulate adhesions and migration of cells. Most implicated adipocytokines in the tumorigenesis pathway are adiponectin, leptin, tumour necrosis factor- $\alpha$  (TNF- $\alpha$ ), Interleukin-6 (IL-6) and Insulin-like growth factor 1 and 2 (IGF 1 and 2).

Adipocytokine related signalling pathways are important in the development of an inflammatory microenvironment for tumours. This process is thought to increase the risk of endometrial cancer by inducing cell proliferation and preventing cell apoptosis. Adiponectin, the most abundant adipokine, has been suggested to have anti-angiogenic, anti-inflammatory, and anti-apoptotic properties. Raised leptin levels in obese state promotes inflammation by stimulating the production of IL-6, TNF $\alpha$  as well as IL-1 and IL-12. Leptin and adiponectin secretion is counter-regulated in vivo. A study by Luhn et. al. has shown adiponectin to have inverse relationship with the risk of endometrial cancer and leptin to have a direct co-relation.

Also, in an inflammatory environment, macrophages secrete potent proinflammatory cytokines such as TNF- $\alpha$  and IL-6, which are known to activate numerous transcription factors that regulate the expression of genes involved in immune responses, anti-apoptosis,

angiogenesis, and metastasis. The mechanisms of tumorigenesis are thought to be involved are free-radical production that cause DNA damage and impaired DNA repair.

Research have further suggested that systemic levels of insulin-like growth factor (IGF) is dysregulated in obesity either due to increased IGF production or by down-regulation of IGF binding protein (IGFBP) prodution. IGF 1 is a growth and proliferation promotor and has inhibitory effects on cell death and is a major contributor in many neoplastic transformation.

The above biomarkers are physiologically interrelated and are likely to reflect a more restricted number of underlying biological pathways. Possibly, they work in a synergistic capacity to modulate the risk of developing endometrial cancer. If specific patterns of cytokine expression were found to be predictive of adverse outcome, then the specific receptors may be targeted as a therapeutic option for endometrial cancer. No study so far has looked at all these markers together in the serum and tissue samples of the same endometrial cancer patients to give a more wholesome idea about their effect on tumour genesis, progression and outcome. Therefore, this study is designed to assess the prognostic significance of these six biomarkers in the blood and tissue of endometrial cancer patients and co-relating the levels with their BMI and tumour type, after adjusting for age, parity, smoking status, menopausal status, use of Hormone Replacement Therapy (HRT)/ hormonal contraception, and prevalence of diabetes and hypertension.

## 2. RATIONALE

Development of novel biomarkers for a variety of uses including diagnosis, treatment monitoring and prognostication is on the Cancer Reform Strategy agenda and actively encouraged by the National Cancer Research Institute and Medical Research Council.

Understanding how adipocytokines influence endometrial cancer risk may help to elucidate biological mechanisms important for the observed obesity-endometrial cancer association.

#### 3. THEORITICAL FRAMEWORK

As the incidence of endometrial cancer continues to rise there is a health need for a better diagnostic and prognostic approach.

Studying the different biomarker levels in blood and cancer tissue will enable us to look for new targets that may be useful in the treatment and prognostication of this cancer.

Also, if the levels of these markers change significantly post-treatment, we can investigate if it will be possible to use these markers to assess response to treatment as follow-up for risk of recurrence forms an important part of the treatment protocol.

### 4. RESEARCH QUESTIONS / AIM(S)

# 4.1. Objectives

To assess the relationship between the endometrial cancer and blood and tissue biomarkers in patients referred for endometrial cancer management to Royal Surrey NHS Foundation Trust.

# 4.2. Primary Outcomes

- To assess the circulating levels of adiponectin, leptin, tumour necrosis factor alpha (TNFα), interleukin 6 (IL-6), Insulin like growth factors 1 and 2 (IGF 1 and 2) in blood and at tissue level (endometrial tissue, adipose tissue, lymph node) from women with endometrial cancer (study population) and in the blood +/- endometrial tissue (control population) and to compare the results between the two groups.
- Additional tests on the samples collected looking at the cancer tissue
  microenvironment for infiltrating inflammatory cells +/- their secretions or other
  adipocytokines. We may also look at the tumour microbiome to look for any
  commensal bacteria or micro-organism and if available, to compare with tissue
  micro-environment and microbiome of normal endometrial tissue from control
  population.
- 3. To determine whether there is a correlation between these markers and obesity (classified by WHO category of BMI) after adjusting for confounding factors like age, parity, menopause, use of HRT/ hormonal contraception, smoking, diabetes and hypertension.

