# **STUDY SUMMARY**

STUDY TITLE	Adipocytokines and their relationship with		
	obesity and endometrial cancer		
SHORT TITLE	Adipocytokines in endometrial cancer		
STUDY DESIGN	exploratory biomarker study		
STUDY PARTICIPANTS	Study population - patients presenting to		
	Royal Surrey NHS Foundation Trust with		
	endometrial cancer, identified at the MDT		
	Control population - female patients		
	without endometrial cancer, referred for		
	benign condition.		
PLANNED SIZE OF SAMPLE	100-120		
FOLLOW UP DURATION	N/A		
PLANNED STUDY PERIOD	36-48 months		
RESEARCH QUESTION /AIM(S)	To investigate the relationship between		
	adipocytokine level in blood and tissue		
	(endometrial cancer tissue, adipose tissue		
	and lymph node) in patients with		
	endometrial cancer and co-relate with BMI		
	to identify peripheral biomarkers that can		
	be used as prognostic or diagnostic tools		

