### 5. STUDY DESIGN and METHODS of DATA COLLECTION AND DATA ANALYSIS

# 5.1. Study design

All patients being referred to the Royal Surrey NHS Foundation Trust with diagnosed uterine cancer will be given the research information leaflet and invited to participate as the study

population of the research. Female patients being referred to Royal Surrey NHS foundation Trust for benign conditions (specifically not endometrial cancer) will be invited to participate as the control population.

Initially, an invitation letter will be sent alongside the patients' clinic appointment letter to inform them of the study and give them time for preliminary consideration of the study. Patients will then be approached in the outpatients' clinics after the initial consultation by the clinician. Alternatively, patients may be approached over phone and information about the study given at that time. The call will be scheduled after the clinic appointment visit so that the patient will have received the Invitation Letter that is sent out with the initial Appointment Letter, allowing patients sufficient time to consider the study. Patients will be given a participant information leaflet detailing the study rationale, methodology and analysis in clinic or alternatively the leaflet will be sent by post/ email (in case of telephone consultations). Patients who agree to participate in the study will be asked to sign a consent form after explanation at a later appointment.

Demographic data will be collected at the same time to correlate various risk factors associated with the development of uterine cancer. The data collected will include age, parity, smoking status, menopausal status, medications used, use of Hormone Replacement Therapy (HRT)/ hormonal contraception, and prevalence of diabetes and hypertension. This data will be collected by:

- Taking a medical history from the patient in clinic
- Patients' medical notes

This data will be directly entered into an existing departmental database for Gynaecological oncology which is password protected and stored on NHS computers.

Study participants will then have 30mls (2 ½ tablespoons) of venous blood taken on the day of the surgery and control participants will also have 30mls of venous blood collection alongside their clinic appointment.

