### 5.5. Data analysis

Standard statistical analytical tools will be used to analyse the data. Relation between different variables will be sought with odds ratio, confidence interval and significance with P value (<0.05 significant). The Mann–Whitney U test will be used to assess differential expression of immune markers between tissue types –blood and tumour tissue. Correlation with clinical characteristics will be determined using univariate log-rank and multivariable Cox proportional hazards adjusting for age, stage, grade and histology. Results will be compared between the study and the control populations.

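### Primary outcome 3 ties BMI to WHO categories with no adjusted model named; coarsening BMI costs power, from about 2 points to nearly half, depending on how the categories are used

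*Combined protocol and SAP*

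**What the plan says.** Section 4.2 lists, as the third primary outcome, the "correlation between these markers and obesity (classified by WHO category of BMI", after adjustment for age, parity, menopause, hormone use, smoking, diabetes and hypertension. It does not say how many WHO categories are used or whether they are treated as ordered.

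Section 5.5 states: "Relation between different variables will be sought with odds ratio, confidence interval and significance with P value", with 0.05 as the threshold. It assigns the Mann–Whitney test to blood versus tumour tissue. It also says: "Correlation with clinical characteristics will be determined using univariate log-rank and multivariable Cox proportional hazards adjusting for age, stage, grade and histology". Those adjustment variables are not the outcome 3 confounders, apart from age. No correlation coefficient, linear model or ordinal model is named.

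Elsewhere BMI appears without categories: the Study Summary has "endometrial cancer and co-relate with BMI" and section 1 has "co-relating the levels with their BMI and tumour type". Section 5.4 measures blood markers by ELISA, which gives a level, and scores tissue markers on immunostaining. Section 7.3 aims for 30–60 cases and 100–120 women in all. Section 5.1 says "The data collected will include age, parity, smoking status, menopausal status, medications used" and continues with hormone use, diabetes and hypertension; BMI, height and weight are not listed.

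**The concern.** BMI and an ELISA level are both continuous. Replacing BMI by a category treats women at the two ends of a category as identical. If the categories enter as unordered groups, several degrees of freedom are also spent on sparse extreme groups. With at most 60 cases, a real marker–BMI association could be missed on a primary outcome for no gain. Because the coding and the model are both open, they could also be settled after the data are seen.

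A second, conditional issue is that cancer/control status is not among the confounders named for outcome 3. The study expects markers to differ between the groups, and section 1 links obesity to endometrial cancer. If cases and controls were pooled without a group term, those two differences together would look like a marker–BMI association.

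**Working it through.** The plan gives no power, effect size or standard deviation, so there is no figure of its own to reproduce.

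**Inputs from the documents:** n=60 (top of the case range, or 30 cases plus 30 controls); n=120 (top of the total); seven covariates (section 4.2); alpha 0.05 (section 5.5).

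**Assumptions:** two-sided test; marker–BMI correlation r=0.3; BMI lognormal with median 29 and log-SD 0.22; WHO cut-points 18.5, 25, 30, 35 and 40; covariates independent of marker and BMI; log blood marker roughly normal.

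**Step 1. Continuous BMI.** Power = Φ(atanh(r)·√(n−3−7) − 1.96), with atanh(0.3) = 0.3095.
- n=60: 0.3095 × √50 = 2.189; 2.189 − 1.96 = 0.229; power 59%.
- n=120: 0.3095 × √110 = 3.246; 3.246 − 1.96 = 1.286; power 90%.
- n=30 (lowest case count): 0.3095 × √20 = 1.384; 1.384 − 1.96 = −0.576; power 28%.

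**Step 2. Same setting by simulation, changing only how BMI enters.**

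| BMI coding (marker continuous, seven covariates) | n=60 | n=120 |
|---|---|---|
| Continuous | 59% | 90% |
| WHO categories, ordered trend | 57% | 88% |
| Obese yes/no | 41% | 73% |
| WHO categories, unordered | 33% | 66% |

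If the marker were also cut into high/low and set against obese yes/no in an unadjusted 2×2 table, power would be about 31% at n=60 and 57% at n=120.

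**Step 3. Sensitivity to r, closed form, no covariates.** Splitting BMI at its median multiplies r by √(2/π) = 0.798. Splitting both at the median gives P(both high) = 0.25 + asin(r)/(2π). For r=0.3 that is 0.298, so 60% against 40% have a high marker.

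| n, r | Both continuous | BMI split | Both split |
|---|---|---|---|
| 60, 0.2 | 33% | 23% | 17% |
| 60, 0.3 | 65% | 45% | 32% |
| 60, 0.4 | 89% | 70% | 53% |
| 120, 0.3 | 92% | 75% | 57% |
| 120, 0.4 | 99.6% | 95% | 83% |

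The loss is large at small n and modest r, and shrinks as either grows.

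**Step 4. Pooling without a group term, no true BMI effect.** With equal groups, a marker shift s and a BMI gap g (both in SD units) induce a correlation of 0.25sg / √[(1+0.25s²)(1+0.25g²)]. Neither s nor g is in the documents; s = 0.5–0.8 and g = 0.4–0.8 are assumed.
- s=0.5, g=0.4, n=60: 0.05/1.051 = 0.048; 0.048 × √50 = 0.34. Rejection is Φ(−1.62) + Φ(−2.30) = 0.053 + 0.011, about 6%.
- s=g=0.8, n=120: 0.16/1.16 = 0.138, atanh 0.139; 0.139 × √110 = 1.46. Rejection is Φ(−0.50), about 31%.

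Simulation agrees: roughly 6% to 30% across these settings, and about 5% once the group term is in.

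**The case against.** The strongest objection is that the plan does not commit to the costly analyses. Several parts of this stand.

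- A reader might infer that naming an odds ratio means the markers will be cut into high and low. The documents do not support that. No marker cut-point is stated, and logistic regression on a continuous marker or a proportional-odds model on WHO categories also yields an odds ratio. Dichotomising is permitted by the text, not prescribed.
- A reader might infer that using WHO categories halves the power. An ordered trend loses only about 2 points, and correlation with ordered categories is a natural reading. Near-halving needs small n together with unordered groups or an unadjusted 2×2 table, and the latter is not the adjusted analysis that section 4.2 calls for.
- A reader might infer that outcome 3 is biased by pooling. The confounder list is given as examples, and both the Study Summary and section 1 place the BMI correlation within endometrial cancer patients. On a cases-only reading there is no pooling bias.
- Tissue markers are scored, so an argument from continuous marker values covers blood only.
- The background figure, "endometrial cancer risk is 16% higher per 5 kg- gained during adulthood", concerns weight gain and cancer risk in a cited review. It says nothing about how this study should model its markers.
- The study calls itself exploratory and states no power target.

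What the objection does not remove is that WHO classification is written into a primary outcome, no adjusted model is attached to it, and a method that loses nothing is available.

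**Conclusion.** The point holds as one of analysis choice. Primary outcome 3 coarsens BMI, and section 5.5 gives no adjusted model for the marker–BMI association. Under the stated assumptions the power lost at n=60 is about 2 points with an ordered trend, 18 with obese yes/no (59% to 41%) and 26 with unordered groups (59% to 33%). At n=120 it is about 2, 17 and 24 points. These figures depend on the assumed correlation, BMI distribution and independent covariates; the direction does not.

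The group-term issue is conditional. It applies only if cases and controls are pooled, and its size (about 6% to 30% false positives instead of 5%) rests on shifts that the documents do not give.

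This should be settled before the data are analysed. It does not threaten the study as a whole.

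**What to change.** Amend sections 4.2 and 5.5 as follows.

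1. **Blood markers:** regress log marker on continuous BMI with the listed confounders and a check for curvature. Report the ratio of geometric means per 5 kg/m² with a 95% confidence interval.
2. **Scored tissue markers:** use an ordinal model with continuous BMI.
3. **WHO categories:** keep them for a descriptive table.
4. **Population:** state whether outcome 3 uses cases only or all women. If pooled, include a cancer/control term and show each group's slope.
5. **Odds ratios:** wherever one is reported, enter the marker as a continuous value.
6. **Data:** add the BMI value to the list in section 5.1, and say how archival cases without a recorded BMI will be handled.

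The cost is mainly wording, with no new samples or assays. A WHO category already requires BMI, so for newly recruited women the value should be at hand; for archival cases this has to be checked. The statistical price is a linearity assumption, which the curvature check addresses.

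### Primary outcome 3 adjusts the marker-obesity association for diabetes and hypertension as confounders, although they are plausibly consequences of obesity, so the total association is never estimated

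*Combined protocol and SAP*

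**What the plan says.** Section 4.2, item 3, sets the aim "To determine whether there is a correlation between these markers and obesity (classified by WHO category of BMI"), and completes the sentence with "after adjusting for confounding factors like age, parity, menopause, use of HRT/ hormonal contraception, smoking, diabetes and hypertension". Obesity is the exposure, each marker is the response, and all seven covariates carry the same label of confounder.

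The last paragraph of section 1 (Background) repeats the list, where it covers the tumour's type as well as BMI. It reads: "after adjusting for age, parity, smoking status, menopausal status, use of Hormone Replacement Therapy (HRT)/ hormonal contraception, and prevalence of diabetes and hypertension".

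Four other places bear on the point:

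- Section 1 also states that "patients who are obese tend to have a poorer outcome with more comorbidities than their non-obese counterparts". It names neither diabetes nor hypertension and gives no causal order.
- Section 2 (Rationale) gives the purpose: the work may "help to elucidate biological mechanisms important for the observed obesity-endometrial cancer association".
- Section 5.1 records both conditions as prevalent status from history and notes. It lists no date of onset.
- Section 5.5 names no regression of marker on BMI. Its only multivariable model is "multivariable Cox proportional hazards adjusting for age, stage, grade and histology", which has a different covariate list.

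**The concern.** A confounder of the marker-obesity association is a common cause of obesity and the marker, or stands in for one. A condition that obesity brings about, and that then changes the marker, is a mediator. Adjusting for a mediator takes out the part of the obesity effect that passes through it. What is left is a narrower quantity, the association not explained by that condition.

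If diabetes and hypertension are at least partly downstream of obesity, outcome 3 as written delivers only the narrower quantity and presents it as control of confounding. The stated purpose is to explain the link between obesity and endometrial cancer, and for that the overall marker-obesity association is of direct interest. A reader of the results would not have it and could not recover it from the planned analysis.

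There is a second, smaller risk. If an unmeasured factor affects both diabetes and a marker, adjusting for diabetes can distort even the narrower quantity.

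**Working it through.** **Figures in the plan.** There is none to reproduce. The protocol gives no effect size, SD or power for outcome 3, and no association between either condition and any marker. Every input below is an assumption, chosen to show direction and rough scale.

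**Set-up.** Obesity O is simplified to yes/no, with half the women obese. D is diabetes and H is hypertension. The marker is in residual SD units:

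marker = b·O + g·D + g·H + error

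- b = 0.5 is the direct effect of obesity.
- g runs from -0.5 to +0.5 and is the shift due to each condition.
- Hypertension prevalence is 30% in non-obese and 55% in obese women, a difference ΔH = 0.25.
- Diabetes prevalence is 10% in non-obese and 20%, 30% or 40% in obese women, so ΔD = 0.10, 0.20 or 0.30.

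**Formulas.** Without D and H in the model, the obesity coefficient is the total: b + g(ΔD + ΔH). With them, it is b = 0.5. The relative change is b/total - 1. Example: g = +0.5 and ΔD = 0.30 give a total of 0.5 + 0.5 × 0.55 = 0.775, and 0.5/0.775 - 1 = -35%.

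| g | Total (ΔD 0.10 / 0.20 / 0.30) | Adjusted | Change |
|---|---|---|---|
| +0.5 | 0.675 / 0.725 / 0.775 | 0.50 | -26% / -31% / -35% |
| +0.2 | 0.57 / 0.59 / 0.61 | 0.50 | -12% / -15% / -18% |
| 0 | 0.50 / 0.50 / 0.50 | 0.50 | 0% |
| -0.2 | 0.43 / 0.41 / 0.39 | 0.50 | +16% / +22% / +28% |
| -0.5 | 0.325 / 0.275 / 0.225 | 0.50 | +54% / +82% / +122% |

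Least-squares fits to 1,000,000 simulated records agreed to within random error. The largest gap was +124% against +122%, in the last cell.

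**Unmeasured common cause.** A second simulation used diabetes only and added an unmeasured standard normal factor U. The log-odds of diabetes were -2.2 + 1.35·O + 1.0·U. U shifted the marker by ±0.5 per unit, diabetes shifted it by -0.3, 0 or +0.3, and the direct obesity effect stayed at 0.5. Adding diabetes to the model changed the coefficient by between -26% (0.555 to 0.411) and +32% (0.443 to 0.586). The adjusted value ran from 0.41 to 0.59, so it missed the direct effect of 0.5 as well as the total.

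**Reading.** The adjusted coefficient differs from the total whenever the conditions depend on obesity and affect the marker. The sign of the difference follows the sign of their effect on that marker.

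**The case against.** **The stated question is the adjusted one.** Item 3 does not stop at a correlation with obesity; the adjustment clause is part of the same sentence. No total-effect target is declared, so an association independent of comorbidity may be what the sponsor wants. This stands in part: it rules out calling the plan's estimate biased without qualification. But the plan calls the two conditions confounders, never says that it seeks a direct association, and plans no model without them.

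**The causal order is not in the documents.** This stands. The Background remark about comorbidities supports it only indirectly. With prevalent status and no onset dates, either condition could be part mediator and part marker of a shared cause. Reporting both models is useful for that reason. The order of parity, menopause, HRT and smoking relative to obesity is not documented either; keeping them in the main model follows the sponsor's list and is not a proof that they come first.

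**Two stronger readings are tempting.** A reader might infer that the adjustment biases outcome 3 towards no association. That holds only for markers that the conditions move in the same direction as obesity, and the documents give no sign for any of the six. A reader might also infer a definite loss of power. The documents give no effect size or SD, and do not say whether outcome 3 uses the 30-60 cases or the planned total of 100-120, so no power figure can be attached to it.

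**The larger gap is the missing model.** Section 5.5 names no marker-BMI regression, and the covariate list in 4.2 reads as illustrative. This is fair, and the repair must reach 5.5 as well.

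**Conclusion.** The point holds in limited form. Outcome 3 labels diabetes and hypertension as confounders of the marker-obesity association, and no analysis without them is planned. If they are even partly consequences of obesity, the only planned estimate leaves out whatever runs through them, and the total association goes unreported.

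The direction is not fixed: towards no association, unchanged, or away from it, marker by marker. The illustrative sizes (12% to 35% smaller, or 16% to 122% larger) rest entirely on the assumed prevalences and effects in the working and are not estimates for this study.

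For an exploratory biomarker study this is an inexpensive improvement to a primary outcome. It does not threaten the study as a whole.

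**What to change.** - **Section 4.2, item 3:** state that the main marker-obesity model adjusts for age, parity, menopausal status, HRT/hormonal contraception and smoking. Add a second model that also includes diabetes and hypertension, labelled as the association not explained by these comorbidities.
- **Section 5.5:** write both regressions in, since none is specified there for marker against BMI, and say which quantity each one estimates.
- **Section 1, last paragraph:** change the covariate list for the BMI association only. The mediator argument does not obviously carry over to tumour type, so leave that part as it is.

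The comparison of cases with controls in outcome 1 is not affected; that item names no adjustment.

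The cost is a wording change and one extra model per marker, using data already collected. The downside is two estimates per marker to present. The sponsor's own specification stays visible as the second model.
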